5. STUDY INTERVENTIONS

5.1 Interventions, Administration, and Duration

5.1.1 Self-Administered Hypnosis Intervention

Participants in the self-administered hypnosis intervention group will be given booklets on the use of hypnosis for the treatment of hot flashes; and be provided with accompanying audio recordings containing hypnosis inductions as described above in Table 3. The booklets provide patient-education about hot flashes and treatment options, and include weekly instructions for a six-week long structured self-administered hypnosis intervention program for the treatment of hot flashes. A one-week baseline period will include the daily hot flash diary completion for the baseline week. During the baseline week, participants will also collect the physiologic measures, saliva three times per day over two consecutive days, and correspondingly, wearing the HRV monitor for 24 hours one day and for two 6 minute supine recordings on the other day. The physiologic measures will be optional for participants using phone or video conference for the baseline visit due to COVID-19 restrictions. Participants will then be asked to listen to audio-recordings of hypnosis inductions designed for the treatment of hot flashes, daily throughout 6 weeks. Each recording will be about 20 minutes long. Practices using the recordings will be documented on the Hypnosis Practice Log.

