6.2.1 Screening Evaluation

Inclusion/Exclusion Criteria Screening Checklist

This brief evaluation may be conducted over the phone and occurs to establish probable eligibility for the study. Questions are asked to confirm that the candidate meets the inclusion/exclusion criteria for the study, using a YES/NO format, and the 4-item PHQ-4 brief screening tool.

The PHO-4 will be completed to assess exclusionary criteria of a PHO-4 score > 9. This brief screening measure was developed from the PHQ-9 and GAD-7 to be an ultra-brief screening tool for depression and anxiety disorders.^[80] It has been validated in the general population and found to be comparable to the PHO-8. [81] Scores on the PHO-4 range from 0 to 12, with scores 0-2 being normal; 3-5 indicating mild symptoms; 6-8 moderate symptoms; and 9-12 severe. Cronbach's alpha for the 4 items was 0.85. The PHQ-4 was strongly correlated with the mental health subscale of the SF 20 (r=.80) and social functioning (r=.52). These correlation coefficients were nearly identical to those of the PHO-8. [80]

samples will be collected over 2 days, upon awakening, 30 minutes later and a bedtime (around 10 pm); Note: this will be optional during* COVID-19 restrictions

^{**}data will be collected during the same two days as cortisol sample collection; Note: this will be optional during COVID-19 restrictions

^{*}EHS will be done during randomization/education visit; Note: EHS-CF will be administered if visit is by telephone or video conference

Individuals scoring ≥9 on the PHQ-4 will be provided with additional referral information. At the University of Michigan, a referral will be made to psychology or psychiatry and the participant's oncologist will be notified, if applicable. There is also an oncall psychiatrist available Monday through Friday from 8 a.m. to 5 p.m. to assist with crisis situations. After hours, an on-call consultant can be reached by calling the clinic operator and arrangements can then be made to have the patient seen in the Emergency Room if necessary by the on-call psychiatrist. At Baylor University, a referral will be made to the Baylor Psychology Clinic (which is open Monday through Friday from 8 a.m. to 7:30 p.m.), Baylor Scott and White Health Center, or community medical health services. After hours, participants will be referred to the Emergency Room at Baylor Scott and White Health Center. (See Section 7.2).

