Each participant will be provided a kit with salivettes for the collection of saliva. Saliva will be collected three times a day over a two consecutive day period at baseline and 6 weeks. Participants will be provided specific directions for the collection of saliva upon awakening, (before getting out of bed), 30 minutes later (before eating, drinking or tooth brushing), and finally at bedtime (around 10 pm, also before tooth brushing) and will be given a Saliva Collection Diary with questions to answer surrounding their saliva collection. Participants will also be instructed to complete Daily Health Behaviors questionnaires during the same two-day period. (This procedure is well established and is considered valid for the measurement of diurnal cortisol rhythm.)^[67, 68]

Cortisol collection is explained in the baseline visit. During the COVID-19 restrictions, this interaction will occur by telephone or video conference. If the participant is unable to demonstrate understanding of the collection process, we will not collect cortisol on that participant in the study. Additionally, if there is any interruption to mail service or to the lab where specimens are banked, this portion of the study will be paused during COVID-19 restrictions.

Measures of Heart Rate Variability

The shift in autonomic balance from sympathetic dominance (stress response) to parasympathetic dominance (relaxation response) is a very likely candidate for the underlying mechanism of the effects of mind-body interventions on vasomotor symptoms. Relatedly, an increasing body of evidence indicates that hot flash events are associated with changes in heart rate variability. [90-92] The Polar V800, a mobile HRV recording device will be worn to collect data over a 24-hour natural ambulatory period as well as two 6 minute supine recordings during the two days of cortisol collection at baseline and 6 weeks. The 24 hr and two 6 minute measurements will be completed (each on separate days) at preand post-trial. The Polar V800 has been shown to have equivalency for the time domain of HRV. [93]

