6.2.3 Follow-up Visits

Week 1-6: Eligible participants will be randomly allocated to either a self-administered hypnosis group or a self-administered sham white noise hypnosis control group. Both groups will meet with a study research assistant two times (at baseline and at randomization/education visit) in person (or by telephone or video conference during COVID-19 restrictions) and further contact will be by phone through week 6 of the intervention period.

The interventions will be delivered through pre-recorded digital audio files, flash drives or CD's. For participants who prefer a flash drive or CDs, those will be provided. Additionally, if a participant prefers to use CDs, but does not have a CD player, one will be provided. Prepared self-management booklets will also be provided to each participant.

Participants in the self-administered hypnosis group and the self-administered sham white noise hypnosis group will use the self-management materials (booklets and audio recordings) for six weeks. A second kit to collect saliva and a Polar V800 HRV monitor will be mailed to participants during week five to be used for Week 6 data collection. At the end of Week 6, they will collect two days of saliva samples. HRV data will also be collected during the two days of saliva collection (as done during the baseline week) and both will be returned immediately following collection via a pre-posted mailer. However, if this collection was optional or unable to be completed due to COVID-19 restrictions, saliva samples and HRV data will not be collected at this time. At the end of Week 6, participants will return the completed hot-flash daily diaries, the self-hypnosis practice log, the questionnaire booklet with outcome measures of daily activity interference, quality of life, sleep disturbance, anxiety and stress in the provided pre-posted mailer. Due to COVID-19 restrictions, participants will also have the option of returning materials electronically (e.g., through DocuSign).

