9.2 Secondary Objectives

Secondary objectives are to evaluate the efficacy of the self-administered hypnosis compared to self-administered sham white noise hypnosis for hot flash activity interference, sleep disturbance, anxiety and perception of benefit; with the expectation that there will be significant improvements among participants in the hypnosis group when compared with the self-administered sham white noise hypnosis group. Further, we will evaluate the effects of self-administered hypnosis compared to the self-administered sham white noise hypnosis control at 12 weeks. In order to obtain estimates of the efficacy of the self-administered hypnosis that is not positively biased on the secondary outcome measures, each secondary outcome measure will be analyzed using intent-to-treatment analysis

Hypothesis 2.1

Compared to self-administered sham white noise hypnosis, self-administered hypnosis will result in significant improvements in hot flash activity interference, sleep disturbance, and anxiety at 6 and 12 weeks and perception of benefit at 6 weeks.

Outcome Measures:

- Hot Flash Related Daily Interference Scale
- PROMIS Emotional Distress Anxiety Scale
- Pittsburg Sleep Quality Index
- Subject Global Impression of Change

Additionally, mediators (perceived stress, cortisol, and heart rate variability (HRV) and moderators (hypnotizability and practice adherence) of hot flash reduction will be explored to address the following hypotheses:

Hypothesis 2.2

A decrease in perceived stress will be indicated in the self-administered hypnosis group due to the intervention, which will correspond and contribute to further decrease of the hot flash score at 6 and 12 weeks.

Outcome Measure:

Perceived Stress Scale

Hypothesis 2.3

Diurnal salivary cortisol will demonstrate better circadian rhythms (steeper slopes) in those with larger hot flash reductions and in the self-administered hypnosis group compared to self-administered sham white noise hypnosis at 6 weeks.

Outcome Measure:

• Diurnal Cortisol Rhythm

Hypothesis 2.4

Self-administration of hypnosis and greater hot flash reductions will result in higher resting and 24-hour parasympathetic activity, reflected as higher HRV, compared to self-administered sham white noise hypnosis at 6 weeks.

Outcome Measure:

• Heart rate variability monitor

Hypothesis 2.5

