The focus of Aim #3 is to determine the extent to which cortisol levels, HRV, and perceived stress mediate the relationship between group assignment and hot flashes. For each, we will test the null hypothesis that there is no mediation, or indirect effect, of these potential mediators on the hot flashes although we hypothesize that the relationship between group assignment and hot flashes will be mediated by these variables. Measurement considerations are presented for cortisol levels and HRV followed by a description of the mediation analysis plan. Cortisol levels will be evaluated using a commercial immunoassay with chemiluminescence detection by the CLASS lab at the University of Michigan for all samples from Baylor and Michigan. The lower concentration limits are 0.44 nmol/liter with intra- and interassay coefficients less than 8%. Cortisol slopes will be determined by recording cortisol values at three different times of day for each of the two collection days at baseline and at the end of the intervention, week 6. Higher slope values will reflect flatter diurnal cortisol rhythms. If values are found to be non-normal, we will use log transformations. [99] For HRV, we will extract beat-to-beat (NN) intervals from the recordings collected by the Polar S810. From these, we will use the well-validated Kubios HRV analysis software package[100] to calculate time domain indices of parasympathetic activity (standard deviation of NN intervals, SDNN; and root mean square of standard deviation

of NN intervals, RMSSD) according to standard guideline.^[101] These measures cover both short and longer term recordings and will be collected at baseline and the end of the intervention, week 6.

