Mediation analysis will be performed using a nonparametric bootstrap method, to determine how much of the improvement in the primary and secondary outcomes is mediated by psychophysiological effects of the intervention and by changes in perceived stress. The nonparametric bootstrap method provides more statistical power than traditional mediation analysis and does not require the assumption of normality. Within-subject change in HRV, cortisol slopes and perceived stress scores will be tested as mediators. Average causal mediation effects (ACME) and average direct effects (ADE) will be calculated to compare the mediated and un-mediated portion of the changes in the primary and secondary outcomes between groups. We will also test if pre-trial HRV predicts treatment effects, as we expect that women with high SNS activity at baseline will have the most to gain.

Moderator analysis will be performed using the longitudinal regression models described above. The benefit of using the longitudinal regression model for examining moderation is that the unique contribution of each moderator to the variability between people/groups or to the variability across time can be determined.

Missing Data

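### As worded, the week-6 rule bars saliva and HRV collection wherever it was optional, so women seen remotely who volunteered baseline samples yield no cortisol or HRV pair, contrary to Table 4 and section 6.2.2.2

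*Combined protocol and SAP*

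**What the plan says.** Four sets of statements bear on week-6 saliva and HRV.

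- **Who has optional collection.** Section 5.1.1, with the same provision for the control arm in 5.1.2: "The physiologic measures will be optional for participants using phone or video conference for the baseline visit due to COVID-19 restrictions". Section 10.1 has baseline kits and monitors mailed to participants during restrictions.
- **The week-6 rule.** Section 6.2.3 (Follow-up Visits), and again section 10.1: "if this collection was optional or unable to be completed due to COVID-19 restrictions, saliva samples and HRV data will not be collected" at that time.
- **The schedule and measure descriptions.** Table 4 marks saliva and HRV at baseline and at week 6. Its HRV note reads "data will be collected during the same two days as cortisol sample collection; Note: this will be optional during COVID-19 restrictions", and the saliva note likewise calls collection optional. Section 6.2.2.2 plans both measures at baseline and 6 weeks. For remote contact it says of saliva "If the participant is unable to demonstrate understanding of the collection process, we will not collect cortisol on that participant in the study", has a matching sentence for HRV, and pauses collection if mail service (for saliva, also the laboratory) is interrupted.
- **What the analyses need.** H2.3 ("Diurnal salivary cortisol will demonstrate better circadian rhythms (steeper slopes) in those with larger hot flash reductions") is set at 6 weeks, and H2.4 expects parasympathetic activity "reflected as higher HRV, compared to self-administered sham white noise hypnosis at 6 weeks". Section 9.7 says the HRV measures "will be collected at baseline and the end of the intervention, week 6", describes cortisol slopes at the same two points, and adds: "Within-subject change in HRV, cortisol slopes and perceived stress scores will be tested as mediators".

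**The concern.** The week-6 rule is triggered by either of two conditions: collection was optional, or it could not be completed. The first describes a woman's status, not what she did. Under 5.1.1 and 5.1.2 every woman with a remote baseline visit has that status, so one who opted in and returned two days of saliva and HRV is treated like one who declined. A site following the text would not sample her at week 6.

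Her baseline record then adds nothing to a 6-week arm comparison or to a within-subject change. The physiologic sample becomes, in effect, the women seen in person. The multiple imputation in 9.7 could not repair this from data, because no week-6 physiology would be observed in the remote group. Two sites could also read the sentence differently without anyone noticing: section 10.3.4 classes uncollected saliva and unrecorded HRV as missed data rather than deviations. A missed week-6 sample cannot be recovered.

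**Working it through.** **Plan's own figure.** Section 9.3 gives 190 without attrition for an effect of 0.41, 5% type I error, 80% power and 1:1 allocation. A two-sided two-sample t test gives 190 (power 0.803). With 18% attrition, 190 / 0.82 = 231.7, hence 232. Both reproduce. The plan gives no figure for saliva or HRV pairs; it says only that 232 serves all aims and should also suffice for mediation.

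**Side-by-side reading for a remote woman who gave baseline samples.**

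| Source | Week-6 saliva and HRV |
|---|---|
| 6.2.3 (Follow-up Visits) and 10.1 | Not collected, because collection was optional |
| Table 4 and its notes | Scheduled, optional |
| 6.2.2.2 | Planned, unless understanding is not shown or services are interrupted |

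These cannot all be followed.

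**Size, on stated assumptions.** The documents give neither the remote share *s* nor the opt-in rate *o* among remote women. Assume 190 completers, that every in-person completer supplies a pair, and that every remote woman who opts in would supply one if asked.

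- Pairs under the literal rule: 190 × (1 − s)
- Pairs if volunteers are sampled: 190 × (1 − s + s × o)
- Pairs lost to the rule: 190 × s × o
- Standard error ratio: √[(1 − s + s × o) / (1 − s)]

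| s | o | Literal rule | Volunteers sampled | Lost | SE ratio |
|---|---|---|---|---|---|
| 25% | 10% | 142.5 | 147.25 | 4.75 | √1.033 = 1.02 |
| 25% | 50% | 142.5 | 166.25 | 23.75 | √1.167 = 1.08 |
| 50% | 10% | 95 | 104.5 | 9.5 | √1.10 = 1.05 |
| 50% | 50% | 95 | 142.5 | 47.5 | √1.50 = 1.22 |
| 75% | 10% | 47.5 | 61.75 | 14.25 | √1.30 = 1.14 |
| 75% | 50% | 47.5 | 118.75 | 71.25 | √2.50 = 1.58 |

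The ratio depends only on *s* and *o*, so it is unchanged if the total is the 247 in the Preface rather than 232.

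**Power, as illustration only.** At s = o = 50%, a two-arm contrast with effect 0.41 has power of about 0.51 with 95 pairs and about 0.68 with 142.5. The 0.41 was derived for the hot flash score, not for cortisol, HRV or an indirect effect. Much of the shortfall from 0.80 comes from women who decline at baseline, which no week-6 rule can cure.

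**The case against.** The best defence is that the drafters meant optional and not done. In 6.2.3 the sentence follows a reference to collection as carried out in the baseline week, so it can be read as sparing women who gave nothing then. That may well be the intent, and Table 4 and 6.2.2.2 agree with it. A reader might infer that the trial deliberately restricts mechanism work to in-person women; the documents do not support that. But neither statement of the rule contains the qualification, and staff at two sites must apply the words as they stand.

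Further limits stand:

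- Not all of the mediation analysis is affected. Perceived stress is a questionnaire at baseline, 6 and 12 weeks and loses nothing. Baseline HRV alone still serves the planned test in 9.7 of whether pre-trial HRV predicts treatment effects.
- The synopsis lists the mediators as exploratory. The primary outcome, the secondary efficacy outcomes and the 190 and 232 figures are untouched.
- A reader might suspect bias between arms. The rule is the same in both arms and turns on the mode of the baseline visit, before randomization. The harm is to precision and representativeness.
- It is tempting to add that women without baseline data should also be sampled, since H2.3 and H2.4 are stated at 6 weeks. They cannot supply a change score, collection is taught at the baseline visit, and 6.2.2.2 says those who cannot show understanding will not be sampled in the study. Leaving them out is defensible.

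**Conclusion.** The point holds as a conflict in the text with a real cost if the week-6 sentence is followed literally. Sections 6.2.3 (Follow-up Visits) and 10.1 bar a collection that Table 4 and 6.2.2.2 allow. The pairs lost are those of remote volunteers, and they are lost to H2.3, H2.4 and the cortisol and HRV mediators only.

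The size is unknown. Over remote shares of 25%, 50% and 75% and opt-in of 10% to 50%, standard errors are about 2–8%, 5–22% and 14–58% larger than they need be. The upper end requires both a 75% remote share and 50% opt-in, and should not be quoted as an estimate. The counts also assume complete in-person pairs, although section 10.3.4 anticipates some missing samples. The change is worth making because it costs little.

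**What to change.** In 6.2.3 (Follow-up Visits) and 10.1, replace the condition with:

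> Participants who provided baseline saliva will be offered week-6 saliva collection, and those who provided baseline HRV will be offered week-6 HRV collection, whatever the visit mode. Collection remains optional for participants seen remotely and is subject to the understanding, mail and laboratory exceptions in the measure descriptions (6.2.2.2). Participants without baseline data will not be sampled at week 6.

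Align Table 4 and its notes with this. Linking each measure to its own baseline avoids asking for HRV from a woman who gave only saliva. Keeping the offer optional and retaining the exceptions avoids a new conflict with 5.1.1, 5.1.2 and 6.2.2.2.

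The cost is a short passage replaced in two places, plus some additional kits and monitors in the week-five mailing that 6.2.3 already plans.

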6.2.4 Completion/Final Evaluation

Week 12: Before the start of week 12, participants will be telephoned to remind them of the 12 week data collection. The diary, log and questionnaires to be completed that week are included in the toolkit. At the end of week 12, participants will return the completed hot-flash diaries, self-hypnosis practice log, and complete questionnaire booklet that includes the measures of daily activity interference, quality of life, sleep disturbance, anxiety, stress and impression of change in the provided pre-posted mailer. Due to COVID-19 restrictions, participants will also have the option of returning materials electronically (e.g., through DocuSign).

Upon receipt of these measures, the Data Collection Quality Control Form: Study Completion will be completed, signed by the CRC, and countersigned by the PI.

Participants who complete the baseline and 6 week data collection will receive payment (gift card or check) in the amount of \$75 and if they complete the 12 week data collection, they will receive another payment (gift card or check) in the amount of \$50 to maximize retention for the longer data collection efforts.

